## **Introduction**

### ***Chronic hepatitis C***

It is estimated that the prevalence of hepatic C virus (HCV) among the Dutch population is 0.12%, implicating that there are over 19.000 HCV infected patients in the Netherlands. [1] Some 500 patients in the Netherlands die each year as a result of hepatitis B and C infection. [2]

### ***Treatment***

Until 2010, HCV treatment using (pegylated) interferon and ribavirin was associated with low efficacy and severe side-effects. As a result, only a selection of patients were treated and would easily be lost to follow-up. A recent study from Dutch hepatitis treatment centers estimated that up to one hundred chronic hepatitis C patients per center were lost to follow-up. [3][4]

In recent years HCV treatment has dramatically evolved due to the introduction of direct acting anti-virals (DAAs). New interferon-free all oral treatment regimes are now available with an efficacy as high as 95% and negligible side-effects. [5]

As of November 2015 a number of oral HCV targeting drugs have been allowed on the Dutch health care market and are fully reimbursed by the Dutch Healthcare Authorities for all HCV genotypes, independent of fibrosis stage. This recent development signals a new phase in the battle against hepatitis C epidemic and will lead to a significant improvement in prevention of HCV transmission, disease burden, and HCV-related complications.

### ***National Plan***

An initiative of experts from the hepatitis work field and the National Institute of Public Health and Environment (RIVM) has developed a strategy how to systematically move chronic HCV from endemic to an import disease. [6,7] This plan is supported by leading HCV experts in the Netherlands, representatives of the liver patient association (NLV) and biomedical industry. [1,8] One of the main elements of this strategy is focused on tracing chronic hepatitis C patients who are lost to follow-up, in addition to integration of multidisciplinary care in diagnosis and treatment.

### ***Fibrosis***

It is known that chronic hepatitis C patients have an increased risk of developing liver cirrhosis with associated complications such as the risk of hepatocellular carcinoma (HCC). Patients with advanced fibrosis and cirrhosis prior to treatment have a particularly high risk and these patients should be prioritized for treatment. [9]

### ***Issue***

We lack data with respect to the chronic hepatic C population that has been lost to follow-up over the last years. This information would be helpful to assist policymakers from other health care systems to judge whether an active track and trace policy would be beneficial and effective in their environment.

### ***Aim***

This project aims to map their disease course, stage of fibrosis and assess their risk of liver related complications in the population that is lost to follow-up.

### **Objectives**

To coordinate active tracing of chronic hepatitis C patients lost to follow-up.

Primary objective:

- Establish liver fibrosis stage of the lost to follow-up population of chronic hepatitis C patients and comparison with our chronic hepatitis C population in regular care

Secondary objectives:

- Number and percentage (compared to total amount of ever diagnosed hepatitis C patients) of lost to follow-up patients
- Identification of reasons for lost to follow-up
- Provide a template for track and trace of lost to follow-up chronic hepatitis C patients that can be used and followed in other healthcare environments
- To compare patient and disease characteristics, comorbidities and co-medication between traced and regular care populations
- To establish an updated and professionalized registry that contains the complete chronic hepatitis C population. This registry may serve as a tool for clinical follow-up after treatment but will provide answers to important questions such as the interindividual rates of fibrosis regression and risk for hepatocellular carcinoma after viral clearance.

### **Hypotheses**

We hypothesize that liver disease, expressed as fibrosis stage, is more advanced in the lost to follow-up population compared to patients under regular care, because we expect there is an overrepresentation of a number of disease specific characteristics in the lost to follow-up population such as: advanced liver disease (fibrosis), prior treatment failure (including discontinuation due to severe toxicity), difficult-to-treat genotype, and co-morbidities. Patients diagnosed > 10 years ago have a higher likelihood to be lost to follow-up due to limited treatment options in the past, and/or intolerance to interferon therapy.

Patient characteristics such as socio-economic status and physical and mental health issues (including substance abuse) may contribute to the risk to be lost to follow-up.

### **Study design**

This is an prospective cohort study, which will start as a pilot study in the Radboudumc.

### **Population**

In the pilot phase we aim to trace lost to follow-up chronic hepatitis C patients in the region Nijmegen. This so-called lost population consists of all patients, that in the past have been identified at the Radboudumc but who are currently lost to or have been withdrawn from follow-up. The time-span of

interest will be 2000-2015. We estimate that this project will retrace 100 lost patients through this search.

As a control group a cohort of patients with chronic hepatitis C under regular care will be used. This cohort consists of patients with hepatitis C treated with PEG-interferon, ribavirin and the first generation protease-inhibitors telaprevir and boceprevir between 2011-2015) and those who are or have been treated with new DAAs.

#### Inclusion criteria

-Ever diagnosed with hepatitis C, lost to follow-up

#### Exclusion criteria

-Younger than 18 years  
-Unable to give informed consent

#### Primary outcome

- Fibrosis stage according to elastography (liver stiffness in kPa) and/or liver biopsy (staging according to Metavir)

#### Secondary outcomes

- Number and percentage of (compared to total amount of ever diagnosed hepatitis C patients) of lost to follow-up patients
- Biomarkers of fibrosis: Enhanced Liver Fibrosis Test [10]
- Liver biochemistry prior treatment
- Liver related complications (hepatocellular carcinoma, cirrhosis, variceal bleeding)
- Patient characteristics and socio-economic status
- Reasons for loss to follow-up
- Disease characteristics (mode of infection, genotype, anti-HCV, PCR, viral co-infections (HBV, HIV), treatment attempts)
- Co-morbidities
- Co-medication
- Alcohol use and smoking behavior

#### Contact & Retrieval

- Before start of the project general practitioners will be informed about our initiative via a transmural newsletter.
- After identification, patients that are identified as lost to follow-up will be contacted: We will first ask permission from the general practitioner to contact these patients.
- The principal researchers will conduct contact with patients ourselves to achieve the highest patient response rate. A fulltime PhD student is appointed for coordination of this project.
- We will inform patients with an information and invitation letter in which we give information on the disease and on the new treatment options. We will invite patients at our outpatient clinic for a screening visit. In the invitation letter we make clear we want to give the patient more information by telephone and that we will call them in the week after the letter arrived. By adding the option of telephonic contact with the patients we hope to gain a higher response since we can explain more about new option treatments and answer to concerns of patients directly. Furthermore we will state clearly in the letter that the costs of the screening visit are not part of the national health insurance, therefore patients do not have to pay their own risk for this visit.

We will emphasize the voluntary character of participation to the patients in this letter. Patients can reply with an answer form/by telephone in case they are not interested in participation. We will ask them to explain why they are not interested.

#### Screening visit

- The screening visit will be conducted at the Radboudumc.
- A hepatitis nurse can be reached by patients with questions regarding the screening visit.
- At the screening visit the patient will be given information about treatment options.

- A medical history of the patient will be taken, including co-medication, comorbidities, alcohol and tobacco use. Questionnaires concerning the reasons for loss to follow up and possible treatment difficulties in the past will be performed.
- To assess whether there is still a treatment indication blood samples will be drawn to assess HCV RNA, genotype, liver biochemistry and possible comorbidities. One tube of blood will be stored to assess viral resistance in case of treatment failure. Transient elastography (Fibroscan) and serum Fibrosis markers (ELF) will be performed to further assess fibrosis stage.

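### The only stated instrument for reasons for loss to follow-up is a questionnaire at the on-site screening visit, so as written the reported reasons would describe attenders rather than the whole lost population

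*Combined protocol and SAP*

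**What the plan says.** The Objectives section lists "Identification of reasons for lost to follow-up" among the secondary objectives, and the Secondary outcomes section repeats it as "Reasons for loss to follow-up". The Population section defines the lost population broadly: everyone previously identified at the centre who is now lost to follow-up or was withdrawn from it.

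The route from identification to data runs as follows.

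- **Identification (Methods).** Chart review is described as a way to set aside patients whose infection cleared or was treated effectively. Where a general practitioner requested the serology, that physician is asked for treatment data and medical history.
- **Permission (Contact & Retrieval).** "We will first ask permission from the general practitioner to contact these patients"
- **Letter and telephone call (Contact & Retrieval).** The stated purpose of the call is to explain, answer concerns and raise response: "By adding the option of telephonic contact with the patients we hope to gain a higher response".
- **Refusal (Contact & Retrieval).** "Patients can reply with an answer form/by telephone in case they are not interested in participation". Of these patients the protocol says: "We will ask them to explain why they are not interested".
- **Screening visit.** "The screening visit will be conducted at the Radboudumc", and there: "Questionnaires concerning the reasons for loss to follow up and possible treatment difficulties in the past will be performed".

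The Outcome assessment section adds that data on the primary and secondary objectives are collected across identification, contact, retrieval and screening, without saying which item comes from which phase. The Statistical Methods section has no comparison of attenders with non-attenders and no handling of missing reasons.

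**The concern.** The objective is about why people were lost, and the target is the whole lost population. The one named instrument reaches only those who can be contacted, agree, and travel to the hospital. These people have just shown that they are willing to return to care, so their reasons for having left may differ from those of people who do not come back.

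The question put to decliners does not fill the gap. Why someone turns down this invitation now is a different matter from why their follow-up stopped, possibly years ago. Non-responders, patients who cannot be reached, and patients whose general practitioner refuses permission are asked nothing that the protocol describes.

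At stake is the reading of a descriptive secondary outcome. The Issue section says the information is meant to help policymakers in other health systems judge whether tracing is worthwhile. A list of reasons presented as that of the lost population, but drawn from attenders, could mislead them.

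**Working it through.** **Step 1: sources, side by side.** The protocol gives no attendance rate, sample size or expected frequency for this outcome, so there is no figure to reproduce. The check is first a reading of each place where a reason for loss could be recorded.

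| Group | What the protocol says is asked or recorded | Reason for loss named? |
|---|---|---|
| Attenders | Questionnaire at the screening visit | Yes |
| Active decliners | Why they are not interested | No, a different question |
| Patients reached by telephone | Information and answers to concerns | No |
| Non-responders, unreachable patients | Nothing described | No |
| General practitioner withholds permission | Nothing described | No |
| Charts | Used to exclude cleared or treated patients | No |
| General practitioner, for serology they requested | Treatment data and medical history | No |

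The Outcome assessment statement could cover further collection in any of these rows, but it specifies none.

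**Step 2: what attenders alone can tell us.** Let *r* be the share of the lost population that attends, *p* the share of attenders giving a certain reason, and *q* the unknown share among everyone else. The share in the whole lost population is

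*r·p + (1 − r)·q*.

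Since *q* can lie anywhere from 0 to 1, the worst-case range is from *r·p* to *r·p + 1 − r*. With *p* = 30% (assumed) and a range of assumed *r*:

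| *r* | Lower: *r·p* | Upper: *r·p* + 1 − *r* |
|---|---|---|
| 90% | 0.9 × 0.3 = 27% | 27% + 10% = 37% |
| 70% | 0.7 × 0.3 = 21% | 21% + 30% = 51% |
| 50% | 0.5 × 0.3 = 15% | 15% + 50% = 65% |
| 30% | 0.3 × 0.3 = 9% | 9% + 70% = 79% |

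**Step 3: direction.** The error of the attender figure is *p* − [*r·p* + (1 − *r*)·*q*] = (1 − *r*)(*p* − *q*). With *p* = 30% and *r* = 50%:

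- *q* = 15%: 0.5 × (30 − 15) = 7.5 points too high.
- *q* = 30%: no error.
- *q* = 60%: 0.5 × (30 − 60) = 15 points too low.

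The sign depends entirely on *q*, which the plan as written would not measure.

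**Step 4: comparison with sampling error.** The Population section expects 100 patients to be retraced, without saying whether that means contacted or attended. Taking 100 attenders, the 95% half-width at *p* = 30% is 1.96 × √(0.3 × 0.7 / 100) = 9.0 points. With *q* = 60%, the selection error is 3, 9, 15 and 21 points at *r* = 90%, 70%, 50% and 30%. Under that assumption, selection error matches or exceeds sampling error from about 70% attendance downwards.

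**The case against.** The strongest reply is that the Outcome assessment section already provides for collection in all phases. Reasons for loss are a secondary objective, identification includes chart review, and contact includes a telephone call, so other sources may well be intended. This stands in part. It rules out saying that reasons are collected nowhere but at the visit, or that none is taken from charts; the documents support only that no other source is stated. It does not remove the point, because a general sentence without an item or source gives staff nothing to record and the analyst nothing to report.

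A reader might go further and infer that reasons linked to social circumstances, mental health or substance use will be under-counted. The Hypotheses section does not carry that. It says such factors may contribute to the risk of loss and does not rank them. It also links loss among patients diagnosed long ago to the limited or poorly tolerated treatments of the past. Patients lost for that reason might be more willing to return for newer treatment, or might not. No attendance rate or reason-specific rate is given, so any stated direction or size of bias would be an assumption.

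A reader might also infer that every lost patient's chart is reviewed and a reason could simply be read from it. The Methods section does not say so, and patients tested through a general practitioner may have no hospital record of why follow-up stopped. Nor do the documents say that the frequencies of reasons form part of the track-and-trace template, which is a separate objective.

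Finally, the Ethical considerations and Recruitment and consent sections tie data registration to consent obtained before the screening event. Recording reasons for people who never attend therefore needs approval. That limits the remedy but does not affect the diagnosis.

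**Conclusion.** The point holds as a limited one. The only stated instrument for reasons for loss is the visit questionnaire, active decliners are asked something different, and no question is described for the remaining non-attenders. Followed as written, the plan yields the reasons of attenders. Whether these over- or understate any given reason in the whole lost population cannot be told from the documents.

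The size can only be illustrated. The range of 15–65% rests on two assumed values, 30% of attenders giving a reason and 50% of the lost population attending. It is a worst-case bound, not a forecast. If attendance is high, or attenders and non-attenders resemble each other, the error is small.

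This is a descriptive secondary outcome in a study that starts as a pilot, so the change is an optional improvement. It is best settled before contact begins, because a question not put to decliners at that time is hard to recover later.

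**What to change.** 1. Put the same short, closed item on why follow-up stopped on the existing answer form and in the planned telephone call, with the same response options as in the visit questionnaire. Keep the question on lack of interest as a separate item.
2. Where a chart or general practitioner record is already being consulted, and the ethics approval and consent arrangement permit, code any recorded reason, with an explicit code for unknown.
3. Report reasons by source (visit, telephone or form, record), together with the numbers identified, permitted by the general practitioner, contacted, declined and attended.
4. Where no other source exists, restrict the conclusion to attenders and respondents.

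If the Outcome assessment section was meant to cover such sources, naming them there does part of this work.

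The cost is one line on an existing form, one item in a planned call and, where allowed, one coded field. The downsides are the ethics approval needed to record decliners' answers, a number of unknown codes, and a remaining gap: non-responders without a usable record stay uncovered, as do patients whose general practitioner refuses permission, unless a record can be used.

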#### Treatment advice and follow-up

- After the screening visit patients will be called with the results of the tests performed and a patient-tailored advice concerning treatment indication and options.
- These results will also be sent to the general practitioner of the patient, who will be asked in case of a treatment indication to refer the patient to a consultant in the hospital for treatment. With this referral treatment falls under regular care. The patient will also receive this letter with the results.
- Depending on disease severity and preference of the patient the location of treatment will be decided. The ideal location of healthcare will be decided upon disease severity and preference of the patient. Patients will be followed in regular care according to current guidelines. [11, 12]

#### Outcome assessment

During the phases of identification, contact, retrieval and screening of lost to follow-up patients the data concerning our primary and secondary objectives will be collected. Disease severity of the lost to follow-up group will be compared with a retrospective cohort of hepatitis C patients under regular care and treated in the Radboudumc.

#### Figure 1. Timeline study duration

#### Withdrawal of individual subjects

Patients can at any moment in the study, without justification, decide to stop their participation.

### Safety reporting

Not applicable, since it does not concern an interventional study.

### Statistical Methods

Descriptive analyses will be performed for baseline data (mean  $\pm$ SD, median, interquartile range). The primary outcome difference in fibrosis stage will be tested between the lost chronic hepatitis C group and control group. To compare different characteristics of the groups either a chi-square test, t-test or Mann-Whitney U test will be used, according to the distribution of variables. Differences between groups will be considered significant at  $P$  values  $<0.05$ . Analyses will be performed using the statistical package SPSS, version 22.0 (SPSS Inc. Chicago, IL, USA).

### Power/Sample Size

Not applicable.

### Ethical considerations

Ethical approval from the CMO Arnhem-Nijmegen will be obtained to contact patients. Patients will be asked informed consent for registration of their anonymized data in the Castor database. The Code of Conduct for the Use of Data in Health Research will be taken into account. [13]

### Recruitment and consent

For recruitment procedures see methods of retrieval section.

Informed consent will be obtained of all participants before the screening event. See the informed consent form, attached to the patient information file, for which specific procedures we obtain consent.

### Benefits and risks assessment

As a result of participation in this study the lost to follow-up population could benefit from re-entry in to the regular health care system and if indicated and wanted by the patient treatment of their chronic hepatitis C. The minimal risks of this study (inconveniences of blood withdrawal, possibility of unexpected medical findings) do not outweigh this benefit.

### Compensation for injury

Since this concerns an observational study, with only a single blood withdrawal as invasive measurement and no interventions, we deem it not necessary to conclude a specific participants insurance (proefpersonenverzekering). We request the CMO dispensation for this insurance. The Radboudumc has a liability insurance applicable to all study participants.

### Incentives

There are no incentives for participants. The measurements during the screening event will be financed from a fund we received from MSD. Therefore these costs will not be accounted to the health insurance of participants or withdrawn from their own risk (eigen risico zorgverzekering).

### Data management

Data will be encrypted, and every patient receives an unique code, based on chronological availability of the data. A validated data management program, termed CastorEDC will be used for data storage. This is a web-based data management system with a high security profile through log-in and data-access authorizations. Data-entry is secured with an audit trail. This database can be used as a registry for follow-up (research).

### Storage of residual material

For all patients that participate in the clinical screening one serum tube will be stored for viral resistance measurement in case of treatment failure. If this material will not be used for clinical purposes we can use this residual material for future research. We will request a separate approval for use of this residual material. Material will be stored with the same patient encryption used for clinical data, at the departments biobank.

### Monitoring

We stratify the risk, based on the NFU risk classification in human research, as negligible. This is an observational study with only a single blood withdrawal and not performed in vulnerable patient category. Therefore no on-site monitoring will be necessary. [14]

### Annual progress report

The investigator will submit a summary of the progress of the trial to the accredited METC once a year. Information will be provided on the date of inclusion of the first subject, numbers of subjects included and numbers of subjects that have completed the trial and amendments.

